6.2 Secondary Endpoint Analyses

As this is an open label, Phase I study, secondary endpoints of safety and tolerability will be reported qualitatively. Efficacy will be measured and reported qualitatively by change in Mayo Score, Goebes Histology Index and SIBDQ. As appropriate Student's t test, Mann Whitney U or ANOVA will be used to compare between time points.

1. Active monitoring of UC study patients for TUDCA safety and tolerability

TUDCA has a strong record of safety in several patient populations^{19, 20, 30} (See Detailed Safety Data Review below). However, TUDCA has not been examined specifically in a UC population. Therefore, we aim to define its safety/tolerability in this population through frequent monitoring and symptom assessment as detailed in the study procedures. Adverse events will be categorized according to CTCAE v5.0 criteria and grading.

Infrequent side effects of TUDCA therapy include diarrhea and headache. Our study nurse coordinator will contact all study patients biweekly to assess for any experienced

adverse events. Additionally, in line with WUSM Center for Clinical Trials protocols, patients will have 24 hour access to report suspected Adverse Events. All adverse events or serious adverse events will be recorded and reviewed with treating physician as well as PI. In the event that patients experience an adverse event potentially related to TUDCA, the patient will be offered the option of dose de-escalation or study withdrawal.

TUDCA dose de-escalation strategy: In the setting of a toxicity that the treating physician determines most likely related to TUDCA, we will reduce the dose to 1000 mg (42-50% of initial dose). Common side effects are diarrhea and headache. Since diarrhea is already a symptom implicit to inclusion, we will consider an increase of ≥3 bowel movements/day to be a likely drug toxicity.

Early stopping rules and Dosage Reduction: In the event that ≥50% of patients experience a TUDCA associated side effect or intolerance, we will initiate early study termination or enroll all future patients at the 1000 mg dose. This decision will be made with the guidance of the appointed Data Safety and Monitoring Committee. Full Stopping rules are described in Section 7.4. Note, individual and study stoppage criteria should be applied to these patients as well.

2. Active Monitoring and Management of new elevations in liver transaminases:

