We anticipate that TUDCA therapy will reduce ER stress and promote mucosal healing. As TUDCA has the potential to increase stool frequency, it is important to measure efficacy through objective measures (endoscopy and histology) as well as clinical symptoms. Thus, we will obtain a complete Mayo UC score at weeks 0 and 6 and a partial (no endoscopic subscore) at weeks 2 and 4.32 Biopsies will be obtained at both

endoscopic procedures and objectively scored by the Goebes index. Thus, secondary endpoints will include the following using FDA recommended UC Clinical trial guidelines⁴¹:

- 1) Mucosal Healing: A decrease of at least 1 point on the Mayo endoscopic subscore with a final score of 0 or 1 will be used as a marker of mucosal healing.
- 2) Clinical Response: A decrease in Mayo Score of ≥ 3 points and a decrease in Mayo Score of ≥ 30% from baseline and a decrease in the rectal bleeding score of ≥ 1 or an absolute rectal bleeding score of 0-1.
 - a. Clinical Remission will also be recorded if achieved as defined by a total Mayo Score of ≤2 with no subscore >1 and improvement of endoscopic appearance of the mucosa (Mayo 0 or 1).
- **3) Histologic activity:** *Histologic disease activity.* Colon biopsy samples will be harvested and fixed as described. H&E stained sections will be evaluated for tissue damage and inflammation by a gastrointestinal pathologist in a double-blinded manner, using the simplified Geboes histology index^{34, 35}

We expect that TUDCA treatment will significantly alleviate inflammation in colon tissues, which will be correlated with increased plasma concentration of TUDCA or the deconjugated form UDCA. We will collect stool samples both before and after TUDCA treatment for potential (longer range) studies of gut microbiota composition.

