7.4 Stopping Rules

Individual stoppage criteria-

Based on extensive clinical trial data, we anticipate that TUDCA will be well tolerated. However, patients will be monitored via study visits and phone calls and will permanently discontinue study drug for any adverse event possibly or probably related to study drug that is considered of *moderate or severe intensity*. To define intensity, we will utilize a standard severity rating scale to ensure this safety monitoring plan is enforced in a standardized fashion. Individual subjects should be discontinued for any adverse event rated a Grade 3 or greater in severity on the Common Terminology Criteria for Adverse Events (CTCAE_v5.0 November 2017) scale v, unless it is clearly related to the underlying disease.

For disease specific symptoms (e.g. diarrhea, rectal bleeding) we will consider disease worsening as an increase in >3 points on the Mayo Score to be potentially related to TUDCA and will lower the dose to 1000 mg as described. If symptoms persist or worsen over the subsequent 5 days, the patient will be permanently discontinued from the study.

Study stoppage criteria-

Enrollment of new subjects should be interrupted should 2 or more patients experience CTCAE Grade 3 event, or 1 or more patients experience CTCAE Grade 4 events not clearly related to the underlying disease. Study enrollment may be resumed following review of all available safety data by the investigator and study team and a concurrent opinion that the totality of the data suggests this event is unlikely to be related to TUDCA. The study should be terminated if, following the review of the safety data, it has not been possible to demonstrate that the adverse event has a clear relationship to the underlying disease or associated co-morbidity.

We will initiate early study termination or enroll all future patients at the 1000 mg dose. This decision will be made with the guidance of the appointed Data Safety and Monitoring Committee. Individual and study stoppage criteria should be applied to these patients as well.

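### Sections 6.2 and 7.4 give unreconciled rules for TUDCA-related diarrhea, and the Mayo trigger in 7.4 names no score version and, if items run 0–3, cannot be met by patients with high baseline scores

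*Combined protocol and SAP*

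**What the plan says.** Section 6.2 (Secondary Endpoint Analyses) expects diarrhea as a drug effect: "As TUDCA has the potential to increase stool frequency", it says, efficacy must also be measured objectively. Its safety text gives two instructions. For an event potentially related to TUDCA, "the patient will be offered the option of dose de-escalation or study withdrawal". For toxicity that the treating physician thinks most likely due to TUDCA, the dose falls to 1000 mg, and for diarrhea "we will consider an increase of ≥3 bowel movements/day to be a likely drug toxicity". It then refers onward: "Full Stopping rules are described in Section 7.4".

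Section 7.4 (Stopping Rules) does not repeat the bowel-movement test. It gives two other instructions that can apply to the same patient:

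- Patients will "permanently discontinue study drug for any adverse event possibly or probably related to study drug that is considered of" moderate or severe intensity.
- "For disease specific symptoms (e.g. diarrhea, rectal bleeding) we will consider disease worsening as an increase in >3 points on the Mayo Score", which is treated as potentially related to TUDCA and lowers the dose to 1000 mg. A follow-up rule is attached: "If symptoms persist or worsen over the subsequent 5 days, the patient will be permanently discontinued from the study".

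Section 7.4 also discontinues for Grade 3 or higher events unless they are clearly due to the underlying disease.

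Section 5 builds the complete Mayo score from four items, one of which is stool frequency. Table 1 and section 6.2 schedule the complete score at weeks 0 and 6 and the partial score (no endoscopy) at weeks 2 and 4. Table 1 lists no partial score at week 0. Entry requires a complete score of at least 5 and an endoscopic subscore of at least 1, with no upper limit.

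**The concern.** Diarrhea is both a symptom of the disease and the main expected side effect, so these rules are likely to be needed. Staff who follow 6.2 and staff who follow 7.4 can treat the same patient differently, and neither section says which one governs or that either test is enough.

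The 7.4 trigger has two further problems. It names no Mayo version, although only the partial score exists between baseline and the end of treatment. It also asks for a rise that a single symptom may be unable to produce, and that a patient who starts near the top of the scale has no room to show.

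At stake is who continues at full dose, who goes to 1000 mg and who stops permanently. Section 4.8.4 treats stopping the drug as withdrawal from the study.

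**Working it through.** **Step 1: the rules side by side (documents alone).** Take a patient with possibly related diarrhea, at least 3 extra bowel movements a day, rated moderate, with bleeding and global assessment unchanged.

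| Rule | Result |
|---|---|
| 6.2, potentially related event | Patient offered de-escalation or withdrawal |
| 6.2, bowel-movement test | Likely toxicity; reduce to 1000 mg |
| 7.4, opening rule | Permanent discontinuation |
| 7.4, Mayo rule | No action unless the score rises by more than 3 |

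An offer of dose reduction and a mandatory permanent stop cannot both be followed. The 5-day persist-or-worsen rule is attached only to the Mayo trigger, so it does not follow a reduction made under 6.2.

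**Step 2: inputs for the ceiling check.** The plan states no figure to reproduce. From the documents: four items, entry at total ≥5 with endoscopy ≥1, trigger >3, which in whole points is a rise of at least 4. Assumed: each item runs 0–3, giving a complete maximum of 12 and a partial maximum of 9.

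**Step 3: stool frequency alone.** Largest rise = 3 − baseline item ≤ 3, which is below 4. The trigger cannot be met. If stool frequency and global assessment both rise to 3, the rise is 6 − (sum of their baselines), which reaches 4 only when that sum is 2 or less.

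**Step 4: room left on the scale.**

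- Complete score: 12 − B ≥ 4 requires B ≤ 8. At B = 9 the largest rise is 3.
- Partial against baseline partial: 9 − P ≥ 4 requires P ≤ 5. At P = 6 the largest rise is 3.

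**Step 5: eligible score patterns.** Listing every combination of four 0–3 items with total ≥5 and endoscopy ≥1 gives 158 patterns. These are score combinations, not patient frequencies.

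| Baseline complete score | Patterns | Partial rise of 4 possible |
|---|---|---|
| 5 | 28 | 28 |
| 6 | 34 | 34 |
| 7 | 34 | 24 |
| 8 | 28 | 12 |
| 9 | 19 | 0 |
| 10 | 10 | 0 |
| 11 | 4 | 0 |
| 12 | 1 | 0 |
| All | 158 | 98 |

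On the partial score the trigger is unreachable in 158 − 98 = 60 patterns. On the complete score it is unreachable in 19 + 10 + 4 + 1 = 34. Stool frequency alone reaches it in 0 of 158, and stool frequency with global assessment in 42.

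**Step 6: range for the assumption.**

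- Items 0–2: complete maximum 8; the largest rise from the lowest eligible score is 8 − 5 = 3, so no eligible patient can meet the trigger on the complete score.
- Items 0–4: stool frequency alone can meet it only by going from 0 to 4. The cut-offs move to a complete score of 13 (16 − 13 = 3) and a partial score of 9 (12 − 9 = 3).

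**The case against.** The best defense is that the sections describe two routes to one action: 6.2 handles suspected drug toxicity and 7.4 handles overall disease worsening. Section 7.4 lowers the dose as already described, which points back to 6.2. On that reading, a global-worsening rule that stool frequency alone cannot trigger is not in itself a fault. This is a fair reading, but the text does not state it. It also does not resolve the clash over related moderate events, the missing Mayo version or the ceiling. One could likewise read the opening rule of 7.4 as meaning Grade 3 or above, but the section does not say which grade counts as moderate.

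Four stronger readings are tempting, and the documents do not support them.

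- **That patients with diarrhea are unprotected.** The bowel-movement test, the moderate-or-severe rule and the Grade 3 rule all remain, and section 6.2 gives patients 24-hour access to report suspected events.
- **That the choice of rule alters the study-level stop.** That rule reads "In the event that ≥50% of patients experience a TUDCA associated side effect or intolerance". It counts side effects and intolerance, whatever the Mayo trigger does. Section 7.2 requires all adverse events to be recorded, so the safety record does not depend on the trigger either.
- **That withdrawals would defeat the primary endpoint.** Section 4.8.4 asks withdrawn patients to complete the completion-visit assessments, and the final visit in Table 1 includes endoscopy. Table 2 needs 5.09 patients at 80% power, so six would suffice on the plan's own figures. What remains is that such a biopsy would follow less than 6 weeks of drug, and section 4.8.5 leaves the visit to the investigator's discretion.
- **That a partial score must be set against the week-0 complete score.** The complete score already contains the partial items, so a baseline partial can be derived. The plan only needs to say so.

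**Conclusion.** The point holds as an inconsistency between two safety sections together with a partly unreachable trigger. The inconsistency rests on the documents alone: for a related moderate diarrhea event, 6.2 allows dose reduction and 7.4 requires permanent discontinuation, and two different tests lead to the same 1000 mg step with no stated order.

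The ceiling rests on the assumed 0–3 items. On that scale the worsening rule cannot fire from a baseline complete score of 9, or from a baseline partial score of 6, so it fails for the sickest eligible patients. The pattern counts show how much of the score range is affected and say nothing about how many of the 12 patients will fall there. Because other rules still protect patients, this is a correction worth making to the wording and not a gap in safety cover.

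**What to change.** In section 7.4, state that the dose falls to 1000 mg on **either** of two triggers:

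1. An increase of at least 3 bowel movements a day over a count recorded at week 0 (the existing 6.2 test).
2. Overall worsening on the partial Mayo score relative to the baseline partial, defined as the week-0 complete score less the endoscopic subscore. The clinicians should choose a threshold that high-baseline patients can reach. On 0–3 items, a rise of 2 is possible up to a baseline partial of 7 (9 − 7 = 2), or 146 of 158 patterns against 98 now. That describes reach only and is not a clinical argument for 2.

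Apply the 5-day persist-or-worsen discontinuation to both triggers. State in both 6.2 and 7.4 whether a related moderate event leads to reduction or to discontinuation, and leave the Grade 3 rule as it is. The response and remission definitions do not change.

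The cost is wording in two sections, one baseline stool count and one follow-up call per dose reduction. A lower score threshold may add a few reductions from ordinary disease fluctuation. If the sponsor chooses reduction for related moderate events, that relaxes the present 7.4 rule, so it should be a deliberate clinical decision.

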7.5.1 Internal Data and Safety Monitoring Board

Adverse Events and Serious Adverse Events will be assessed and recorded with oversight by an institutional DSMC (Data Safety and Monitoring committee) that will meet after the 7th patient has completed the study. At that point, the Data and Safety Monitoring Committee (DSMC) will meet to determine whether enrollment may continue to the randomized portion of the study.

In compliance with the Washington University Institutional Data and Safety Monitoring Plan, the DSMC will meet to review toxicity data at least every 6 months. The report will be prepared by the statistician with assistance from the study team and will be submitted to the Quality Assurance and Safety Monitoring Committee (QASMC). This report will include:

- HRPO protocol number, protocol title, Principal Investigator name, data coordinator name, regulatory coordinator name, and statistician
- Date of initial HRPO approval, date of most recent consent HRPO approval/revision, date of HRPO expiration, date of most recent QA audit, study status, and phase of study
- History of study including summary of substantive amendments; summary of accrual suspensions including start/stop dates and reason; and summary of protocol exceptions, error, or breach of confidentiality including start/stop dates and reason
- Study-wide target accrual and study-wide actual accrual
- Protocol activation date
- Average rate of accrual observed in year 1, year 2, and subsequent years
- Expected accrual end date and accrual by arm
- Objectives of protocol with supporting data and list the number of participants who have met each objective
- Measures of efficacy
- Early stopping rules with supporting data and list the number of participants who have met the early stopping rules
- Summary of toxicities separated by arm
- Abstract submissions/publications
- Summary of any recent literature that may affect the safety or ethics of the study

The study principal investigator and Research Patient Coordinator will monitor for serious toxicities on an ongoing basis. Once the principal investigator or the Research Patient Coordinator becomes aware of an adverse event, the AE will be reported to the HRPO and QASMC according to institutional guidelines.

Additionally, if two or more serious adverse events of a similar nature occur and a causal relationship to the investigational product cannot be excluded, accrual to the randomized portion will not occur.

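### After a Grade 3/4 safety pause, Section 7.4 lets the investigator and study team resume enrolment without requiring DSMC review or agreement

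*Combined protocol and SAP*

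**What the plan says.** **The pause (7.4, study stoppage criteria).** "Enrollment of new subjects should be interrupted should 2 or more patients experience CTCAE Grade 3 event". A Grade 4 event that cannot clearly be put down to the disease, in even one patient, has the same effect.

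**Resuming (7.4).** "Study enrollment may be resumed following review of all available safety data by the investigator and study team", together with "a concurrent opinion that the totality of the data suggests this event is unlikely to be related to TUDCA". The text does not say whose opinion must concur. The plain reading is that of the investigator and study team just named.

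**Terminating (7.4).** The study should be terminated if, after the safety review, "it has not been possible to demonstrate that the adverse event has a clear relationship to the underlying disease or associated co-morbidity". No decision-maker is named.

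**The DSMC in 7.4.** For the choice between early termination and enrolling later patients at the reduced dose, 7.4 says "This decision will be made with the guidance of the appointed Data Safety and Monitoring Committee". Section 6.2 ties that choice to a different trigger: at least half of patients with a TUDCA-associated side effect or intolerance.

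**The DSMC in 7.5.1.** "Adverse Events and Serious Adverse Events will be assessed and recorded with oversight by an institutional DSMC". It meets after the seventh patient has completed, and "the DSMC will meet to review toxicity data at least every 6 months". No meeting prompted by a pause is stated. The section refers to institutional DSMC policies for the committee's full responsibilities.

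**The concern.** The decision to restart enrolment turns on a causality judgement, which is hard to make in this trial. Every patient receives TUDCA (4.3), so there is no control group to help attribute an event. Diarrhoea is both a symptom of the disease and a listed side effect of the drug (6.2). The protocol records a firm prior view: Section 6.2 regards human safety as already established and expects minimal adverse effects, and Section 6 credits the co-PI with discovering the drug's therapeutic role in the mouse models.

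Nobody outside the study team is named to judge whether an event is clearly disease-related. The same people may therefore assess causality when the pause is triggered and again when it is lifted. The protocol already has a separate committee with clinicians and a biostatistician, yet its agreement is not needed at this step. At stake is whether further patients are exposed after serious toxicity on the study team's judgement alone.

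**Working it through.** There is no figure in the plan to reproduce; the point is about who decides. Two checks apply.

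**1. Does any other provision require outside agreement before resuming?**

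- *Default to termination (7.4).* It limits the outcome, but names no one outside the team.
- *DSMC guidance (7.4, 6.2).* It covers termination or reduced-dose enrolment. Section 7.4 repeats the sentence without the 50% trigger given in 6.2, so it could be read as following the pause. Plain resumption would still fall outside it.
- *AE reporting to HRPO and QASMC (7.5.1).* This is reporting, not approval.
- *SAE stop (9.1).* A findings report is required before resumption and is shared with the IRB and others. Their agreement is not required, and the DSMC is not named.
- *DSMC report (7.5.1).* It summarises accrual suspensions with start and stop dates, so the committee would learn of a pause, possibly after it had been lifted.

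None makes outside agreement a condition.

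**2. Could a pause be resolved before the DSMC first meets?**

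Inputs: 12 patients (2.1); 2-3 enrolments per month (3.3); completion at 6 weeks (Study Summary duration; final visit in Section 5, Table 1) or 8 weeks including follow-up (2.1). Six weeks is 1.38 months and eight weeks 1.84. Month 0 is the first enrolment, accrual is even, and there are no withdrawals.

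Seventh completion = (7 − 1)/rate + participation. Patients enrolled by then = whole part of (rate × time) + 1, at most 12. Last enrolment = (12 − 1)/rate.

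| Rate per month | Completion | Seventh completes (months) | Enrolled by then | Last enrolment (months) |
|---|---|---|---|---|
| 2 | 6 weeks | 3.00 + 1.38 = 4.38 | 9 | 5.50 |
| 2 | 8 weeks | 3.00 + 1.84 = 4.84 | 10 | 5.50 |
| 3 | 6 weeks | 2.00 + 1.38 = 3.38 | 11 | 3.67 |
| 3 | 8 weeks | 2.00 + 1.84 = 3.84 | 12 | 3.67 |

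The count-based meeting therefore falls at about 3.4-4.8 months, with 9 to 12 of 12 enrolled. A 6-month review, if counted from first enrolment, falls after planned last enrolment (3.67-5.50 months); the protocol gives no start date for that cycle. If enrolment pauses before the seventh patient enters (2.0-3.0 months), the count-based meeting cannot be reached until enrolment resumes.

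**How likely is an early pause?** The documents give no event rates, so these are assumptions. With per-patient probabilities p3 (Grade 3) and p4 (Grade 4) of qualifying events, and q = 1 − p3 − p4:

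P(pause among n) = 1 − [qⁿ + n·p3·qⁿ⁻¹]

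| Assumed p3 / p4 | n = 7 | n = 10 |
|---|---|---|
| 5% / 1% | 0.11 | 0.18 |
| 10% / 2% | 0.27 | 0.41 |
| 20% / 5% | 0.62 | 0.79 |

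For the first row at n = 7: q = 0.94, so 1 − (0.6485 + 7 × 0.05 × 0.6899) = 1 − 0.8899 = 0.11.

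**The two standards in 7.4.** Resumption is allowed if the event is unlikely to be related to TUDCA. Termination is called for unless a clear link to the disease or a co-morbidity is shown. An unexplained event thought unlikely to be drug-related meets both conditions at once.

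**The case against.** The strongest reply is that the team does not act unobserved. AEs go to HRPO and QASMC, SAEs go to the IRB (7.3.1, 9.1), and unexpected fatal or life-threatening events associated with the drug go to the FDA (7.3.2). Section 9.1 requires an investigation and a findings report when an SAE raises risk, and 7.4 leans towards termination. In a 12-patient, single-centre, open-label Phase I study, who signs off may look like a design preference. This stands as a limit on the severity. It does not remove the point, because none of these steps is a precondition for resuming.

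Three stronger readings are tempting, and the documents do not support them.

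- *An independent committee is bypassed.* Section 7.5.1 calls the body internal and institutional. It sets membership and conflict disclosure, but does not say that members are independent of the study. The contrast is between the study team and a separate body.
- *The team is biased because it is unmasked.* All patients receive TUDCA, so the DSMC would be equally unmasked.
- *Nothing can convene the DSMC at a pause.* This holds only for the protocol's own text. The institutional policies cited in 7.5.1 are not available here and may provide for ad hoc meetings. The 6-month interval is also a minimum frequency, so earlier meetings are permitted.

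**Conclusion.** The concern holds in this limited form: the protocol lets the investigator and study team resume enrolment after a Grade 3/4 pause and requires no DSMC review or agreement. Its other safeguards report on, investigate or constrain that decision, without requiring anyone outside the team to agree to it.

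On the planned accrual, the DSMC meeting tied to the seventh completer comes when 9 to 12 of 12 patients are enrolled, so a pause could be resolved before the committee first meets. This rests on even, uninterrupted accrual with no withdrawals; a pause or slower recruitment would move the dates. A reader might infer that an early pause would be lifted. The documents do not say so, since termination is also open. The pause probabilities rest on assumed event rates and show only that an early pause is plausible.

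This is a change that should be made because it is cheap and strengthens safety oversight. It does not show that oversight is absent. The conflict between the resume and terminate standards is a separate textual defect in the same paragraph.

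**What to change.** - In 7.4, require that any pause under the study stoppage criteria go to the existing DSMC for ad hoc review, and that enrolment resume only with its written agreement. The study team supplies the data and its own causality assessment.
- In 7.5.1, add this ad hoc meeting to the stated schedule. If the institutional policies already provide one, cite that provision.
- In 7.4, reconcile the standard for resuming with the standard for terminating, so that one event cannot satisfy both, and state whose opinion must concur.

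These edits alter no dose, grade threshold or patient-level rule. The cost is one ad hoc call of an existing committee per pause and some delay in resuming.

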7.1 Definitions

Adverse Event

An **adverse event** (AE) is any symptom, sign, illness or experience that develops or worsens in severity during the course of the study. Intercurrent illnesses or injuries will be regarded as adverse events. Abnormal results of diagnostic procedures are considered to be adverse events if the abnormality:

- results in study withdrawal
- is associated with a serious adverse event
- is associated with clinical signs or symptoms
- leads to additional treatment or to further diagnostic tests
- is considered by the investigator to be of clinical significance

Serious Adverse Event

Adverse events are classified as serious or non-serious. A **serious adverse event** is any AE that is:

- fatal
- life-threatening
- requires or prolongs hospital stay
- · results in persistent or significant disability or incapacity
- a congenital anomaly or birth defect
- an important medical event

What are serious adverse events or unanticipated problems?

Any incident, experience, or outcome that meets all of the following criteria:

- (1) unexpected (in terms of nature, severity, or frequency) given (a) the research procedures that are described in the protocol-related documents, such as the IRB-approved research protocol and informed consent document; and (b) the characteristics of the subject population being studied;
- (2) related or possibly related to participation in the research (in this guidance document, possibly related means there is a reasonable possibility that the incident, experience, or outcome may have been caused by the procedures involved in the research);
- (3) and suggests that the research places subjects or others at a greater risk of harm (including physical, psychological, economic, or social harm) than was previously known or recognized.

All adverse events that do not meet any of the criteria for serious should be regarded as **non-serious adverse events**.

Adverse Event Reporting Period

The study period during which adverse events must be reported is normally defined as the period from the initiation of any study procedures to the end of the study treatment follow-up. For this study, the study treatment follow-up is defined as 14 days following the last administration of study treatment.

Preexisting Condition

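### Section 7.4: after an enrolment pause, an event judged unlikely to be due to TUDCA, but not clearly shown to be due to the disease or an associated co-morbidity, meets both the resume and the terminate condition

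*Combined protocol and SAP*

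**What the plan says.** The study stoppage criteria in Section 7.4 have three steps.

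- **Pause.** "Enrollment of new subjects should be interrupted should 2 or more patients experience CTCAE Grade 3 event, or 1 or more patients experience CTCAE Grade" (the quote stops just before the number, which is four). The qualifier that follows is "events not clearly related to the underlying disease". Only a clear link to the underlying disease exempts an event here; co-morbidity is not mentioned.
- **Resume.** "Study enrollment may be resumed following review of all available safety data by the investigator and study team", together with "a concurrent opinion that the totality of the data suggests this event is unlikely to be related to TUDCA".
- **Terminate.** The study should end if, after the safety review, "it has not been possible to demonstrate that the adverse event has a clear relationship to the underlying disease or associated co-morbidity".

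The section closes with a further outcome, "We will initiate early study termination or enroll all future patients at the 1000 mg dose", to be decided with guidance from the Data Safety and Monitoring Committee. That paragraph states no trigger. Section 6.2 attaches a similar sentence to a rule that half or more of the patients have a TUDCA-associated side effect or intolerance, and refers to Section 7.4 for the full stopping rules.

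The individual rule in Section 7.4 has a wider grade range: "Individual subjects should be discontinued for any adverse event rated a Grade 3 or greater in severity", unless the event is clearly related to the underlying disease.

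Section 7.1 defines adverse events broadly: "Intercurrent illnesses or injuries will be regarded as adverse events".

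**The concern.** A study-level stopping rule should give one answer once the review has reached its finding. Here the two sentences that follow the pause ask different questions. To resume, the team must think TUDCA an unlikely cause. To avoid termination, the review must positively establish the disease or an associated co-morbidity as a cause. An event can pass the first test and fail the second, and the protocol does not say what happens then.

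Two careful readers could thus reach opposite conclusions about the same event: one restarts enrolment, the other ends the trial. The choice between the sentences would be made after the event is known, and the resume sentence gives the review to the investigator and study team.

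The grade wording raises a second, smaller question. The pause names Grades 3 and 4 only, so on its face the most severe grade does not trigger it.

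**Working it through.** This is a question of logic, and the plan gives no figure to reproduce.

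**Step 1: code the two conditions.** Resume is allowed if TUDCA is judged unlikely. Termination is directed if no clear link to the underlying disease or an associated co-morbidity is shown. Apply both to each finding a review could reach:

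| Review finding | Resume condition met | Terminate condition met |
|---|---|---|
| Clearly the underlying disease (normally no pause) | yes | no |
| Clearly an associated co-morbidity | yes | no |
| Clearly another cause (injury, intercurrent infection, procedure complication) | yes | **yes** |
| Cause undetermined, TUDCA judged unlikely | yes | **yes** |
| Cause undetermined, TUDCA not judged unlikely | no | yes |
| TUDCA likely | no | yes |

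Two of the six findings meet both conditions. This is a count of categories, not a probability.

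**Step 2: check that such events are in scope.** Section 7.1 counts intercurrent illness and injury as adverse events and starts the reporting period at the first study procedure. Table 1 in Section 5 schedules endoscopy at baseline and at week 6, and Section 5 allows up to 12 additional biopsies. Section 4.6 permits background therapy. Events with a cause outside TUDCA, colitis and co-morbidity can therefore enter the rule.

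**Step 3: look for a sentence that settles precedence.** Section 7.4 has none. Section 6.2 defers to Section 7.4. Section 7.5.1 uses a third standard, a causal relationship that cannot be excluded, but ties it to accrual to a randomised portion; Sections 2.1 and 4.3 describe an open-label study in which everyone receives TUDCA. Section 9.1 stops the study, pending investigation, for a serious adverse event that raises the risk to participants, and does not mention the Section 7.4 tests.

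**Step 4: compare the grade wording.** Individual rule: Grade 3 and above. Study-level pause: Grade 3 (two or more patients) or Grade 4 (one or more). Grade 5 is inside the first and, read literally, outside the second.

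**Step 5: illustration only.** The documents give no rates for severe events unrelated to TUDCA and colitis. Let p be an assumed per-patient probability, with n = 12 (planned enrolment). Then P(at least 1) = 1 − (1 − p)^12 and P(at least 2) = 1 − (1 − p)^12 − 12p(1 − p)^11.

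| Assumed p | At least one patient with Grade 4 | At least two patients with Grade 3 |
|---|---|---|
| 0.01 | 0.114 | 0.006 |
| 0.02 | 0.215 | 0.023 |
| 0.05 | 0.460 | 0.118 |
| 0.10 | 0.718 | 0.341 |

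For example, at p = 0.05 the Grade 3 figure is 1 − 0.540 − 0.341 = 0.118 after rounding. The spread from 0.006 to 0.718 shows that the result is set by the assumption. The figures also overstate the conflict: they include events clearly due to a co-morbidity, which create none, and they cover all 12 patients although resumption matters only while enrolment is open. At the 2 to 3 patients a month expected in Section 3.3, 4 to 6 of the 12 would enrol in the last two months.

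**The case against.** The strongest reply is that the sentences can be read together. Resuming is permissive (*may*) and terminating is directive (*should*), so a team that terminates breaches neither. On that reading they are cumulative gates: TUDCA must be unlikely, and a disease or co-morbidity cause must also be shown. Both gates could do work, because Section 7.4 itself treats worsening of disease symptoms as potentially related to TUDCA, and Section 6.2 allows that TUDCA may exacerbate diarrhoea. An event could be tied to the disease and still not be unlikely to be drug-related.

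This reading is coherent, and it rules out the inference that the rule imposes two opposite mandatory outcomes. It does not remove the defect, because the protocol never states it. The resume sentence, taken alone, permits enrolment to restart on the TUDCA test only. One could also stretch *associated co-morbidity* to cover injuries and infections, but the term is undefined, and the undetermined-cause finding would remain in conflict.

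Three other strong readings are tempting and are not supported.

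- **That every Grade 4 event triggering the pause is caught in the conflict.** The trigger is judged before review. Termination is judged after it and adds co-morbidity, so an event may be explained in the meantime. Nor does lack of a clear disease link make TUDCA unlikely.
- **That any severe event due to neither TUDCA nor colitis is caught.** A clear co-morbidity cause meets only the resume condition, and one patient with a Grade 3 event does not start the study-level rule.
- **That a death would leave the study without any stop.** Section 9.1 requires immediate reporting of deaths to the IRB and stops the study for a serious adverse event that increases participants' risk. That stop is conditional, so the gap in the Section 7.4 wording stands but is partly covered.

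It is also fair that Section 7.4 is not the only study-level safeguard, since Sections 6.2 and 9.1 contain others, and that its closing paragraph brings in the committee.

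**Conclusion.** The point holds in a limited form. The resume and terminate conditions overlap for events judged unlikely to be due to TUDCA and not clearly shown to be due to the underlying disease or an associated co-morbidity. For these the text permits one action, directs another, and gives no order between them. The grade wording of the pause is also inconsistent with the individual rule, and Section 9.1 closes that gap only conditionally.

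The conclusion rests on the wording alone and needs no assumption about event rates. A reader might infer from the binomial table that the conflict is a likely path in this trial. The documents do not support that: the rates are assumed, and at 1% to 2% the chance of two or more patients with Grade 3 is only 0.6% to 2.3%. The reason to correct the text is that a stopping rule has to be unambiguous before it is needed.

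**What to change.** Three edits are needed, mainly in Section 7.4.

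1. Reconcile the resume and terminate sentences so that each review finding, including another identified cause and an undetermined cause, leads to one stated action. Alternatively, state which sentence prevails when both conditions are met.
2. Reconcile the grade wording of the study-level pause with that of the individual rule and with the study stop in Section 9.1.
3. Check the revised rule against the six findings tabulated above, to confirm that none leads to two actions.

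Which attribution standard governs, and what action follows it, is for the sponsor to decide. The cost is a few sentences of protocol text, with no added procedures, visits or staff.
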